1 BACKGROUND

1.1 Introduction

Chemotherapy-induced peripheral neuropathy (CIPN) is a common side effect associated with the taxanes and platinum-based compounds, drugs commonly used for the treatment of breast, lung, and ovarian cancer. CIPN results from damage to, or dysfunction of, the peripheral motor, sensory, and autonomic nerves and manifests with a variety of symptoms including mechanical and cold allodynia, numbness and tingling, loss of proprioception, and long-lasting burning pain (1-4). CIPN affects quality of life, and can often result in chemotherapy dose reductions and early treatment discontinuation (5).

Depending on the specific chemotherapy regimen used, the duration of exposure, and method of CIPN assessment, approximately 30% to 70% of multiple-agent, chemotherapy-treated cancer patients are diagnosed with CIPN (6-8). Current CIPN treatment options include duloxetine, tricyclic antidepressants, gabapentin, and topical applications (eg, baclofen and ketamine) (5). However, treatment options to manage CIPN are not consistently effective for the majority of patients. Thus, there is a critical need to identify new agents that can manage the pain associated with CIPN.

This clinical trial is designed to determine if nicotine transdermal patch use can suppress the pain associated with CIPN. Demonstrating that nicotine can suppress such pain would be highly significant on 3 fronts. First, by relieving CIPN-associated pain, suboptimal chemotherapeutic dosing schemes might be adjusted upwards, increasing the probability of effective treatment of the cancer. Second, the use of an FDA-approved, over-the-counter drug with a relatively safe short-term use profile would greatly accelerate the clinical development of this pain management strategy. Third, a demonstration that nicotine can manage the pain associated with CIPN would stimulate the development of targeted agents that interact with subtypes of nicotinic acetylcholine receptors (nAChRs) and which might act with fewer side effects.

1.2 Rationale and Previous Work

This clinical trial will focus on nicotine, the prototype agonist of nAChRs, as a possible agent for symptom suppression of CIPN. The analgesic properties of nicotine and nicotinic agonists have been established in many animal (9) and human studies (10) including neuropathic pain in humans (11, 12). Animal models have been developed that reiterate many of the neuropathological changes and electro-physiological abnormalities observed in patients with CIPN (13). Nicotine has analgesic properties and has been shown to reduce pain in both animal and human studies ((9-12). Nicotine has the advantage of having a well-established risk profile and is relatively safe for short-term use (16). It is also available over-the-counter as a transdermal patch which greatly simplifies drug delivery. These qualities of nicotine provide a strong rationale for using it to treat CIPN-associated pain. Thus, the primary objective of this trial is to test, in cancer stable/remission patients with diagnosed CIPN, the efficacy of acute nicotine transdermal patch administration in assessing clinically subjective improvements in measures of neuropathic pain, as well as improvements in quality of life CIPN patient-reported outcomes (PROs). This study will serve as a proof-of-principle study that could lead to future studies employing more selective nAChR-targeted drugs that are currently in development by our group.

1.2.1 Preclinical Data

Paclitaxel and cisplatin have been shown to produce a long-lasting, bilateral neuropathy in mice, featuring hypersensitivity to mechanical and cold stimuli (14). Consequently, well-established mouse models of CIPN have been used by our group (15), as well as other laboratories to investigate nAChRs as potential targets for amelioration and/or prevention of CIPN. In a dose-dependent manner, nicotine has been shown to reverse the mechanical and cold allodynia induced in rats treated with oxaliplatin (9) and in mice treated with paclitaxel (Figure 1) (16). The doses of nicotine used generated plasma concentrations (20 to 30 ng/ml at doses of 0.6 and 0.9 mg/kg) of the drug, well within the concentration range of nicotine reported for nicotine transdermal patches users. These results strongly support the potential utility of nicotine in mitigating CIPN.

[figure not shown]

Figure 1. Nicotine reverses paclitaxel-induced mechanical allodynia in mice.

Male C57BL/6J mice received 8 mg/kg paclitaxel via intraperitoneal (i.p.) injection every other day for a total of 4 injections. At 2 weeks post-paclitaxel injections, mice received a single i.p. injection of saline or nicotine. Mechanical threshold was determined via von Frey filament testing on the left and right hind paws. Error bars represent the standard error of the mean for one experiment ($n = 6$). A two-way ANOVA revealed significant differences; * $p < 0.05$ vs saline. BL, baseline.

1.3 Study Design

This study will test the efficacy of acute nicotine transdermal patch administration using an open-label, within-subjects clinical trial design with nicotine transdermal patch concentrations of 7 mg and 14 mg. Patients will be recruited via clinician referral and must not have used any nicotine or tobacco products (eg, cigarettes, electronic cigarettes, smokeless tobacco, or other nicotine replacement therapies) within the last 14 days prior to study treatment start date. Each treatment condition will have a duration of 14 days, with a washout period of at least 14 days in between conditions. Patients will be evaluated by the study team once per week during the treatment cycles (2 study visits per treatment cycle). Patients will be evaluated by the study team once during the washout period (1 study visit). Patients will also be evaluated at least once during the 30-day follow-up period (1 study visit). During study visits, patients will be evaluated by the study team for CIPN PROS, pain scale, and Adverse Events (AE). This evaluation schedule will provide complete clinical and research assessments related to pain and neuropathy at baseline, during treatment conditions, and post-treatment.

The primary outcome measure is the change in CIPN-related PRO as measured by the total sensory score of the European Organization for Research and Treatment of Cancer quality of life questionnaire (EORTC QLQ-CIPN-20). EORTC QLQ-CIPN-20 is a well-developed 20-item questionnaire, that provides valuable information on CIPN- related symptoms and functional limitations of patients exposed to potentially neurotoxic chemotherapeutic and/or neuroprotective agents ([17](#)). It has also been validated clinically by showing very significant association between QLQ-CIPN20 scores and the NIH Common Terminology Criteria for Adverse Events (CTCAE) grades for AEs associated with CIPN symptoms ($p<0.0001$), whereby patients with higher CTCAE grade had worse QLQ-CIPN20 scores ([18](#)).

The secondary outcome measures include the following items: 1) the change in average pain based on the well-validated Brief Pain Inventory-Short Form (BPI-SF) average pain severity item; and 2) evaluation of the safety and toxicity of nicotine transdermal patch administration in a population of non-smokers experiencing CIPN.

The BPI-SF contains 4 items assessing average, worst, least, and immediate pain severity in the last 24 hours. Pain severity items are scored using an 11-point numeric rating scale (0, no pain; 10, pain as bad as you can imagine). Seven BPI-SF items will be used to quantify the degree to which pain interferes with daily activities or function (0, does not interfere; 10, completely interferes). The 7 items are summed to obtain a total interference score. The BPI-SF worst pain severity item has been shown to be reliable and valid for use as a single item. We chose average pain severity as an outcome measure based on recommendations from the initiative on Methods, Measurement, and Pain Assessment in Clinical Trials (IMPACT) and other CIPN studies ([19](#)).

Patients will be monitored for nicotine-associated toxicity utilizing CTCAE v5.0. AE assessments will occur at least once per week during treatment conditions.

Exploratory outcome measures include the patient's assessment of the efficacy of a transdermal nicotine transdermal patch for the treatment of CIPN utilizing the Patient Global Impression of Change and Patient Preference Questionnaire (PGIC) for neuropathy (upper and lower extremity questionnaires). The PGIC is used to assess patients' own impressions of change ([20](#)). The questionnaire uses a global scale from "much better"

through “no change” to “much worse” (21, 22). This study will use a version of the PGIC adapted to patients with CIPN that focuses on patients’ self-assessment of their upper and lower extremities. Additional exploratory investigations include: 1) the correlation between serum nicotine levels and efficacy of nicotine transdermal patch administration for the treatment of CIPN in patients whose cancer is stable or in remission; 2) the differences in CIPN PROs and BPI-SF measures between patients that received previous platinum-based chemotherapy versus patients that received previous taxane-based chemotherapy; and 3) the differences in CIPN PROs and BPI-SF measures between never-smokers (nicotine-naïve) and current non-smokers.

The clinical trial will yield several important results. First, using an acute nicotine transdermal patch administration will determine both the potential efficacy and feasibility of using nicotine as a potential treatment for neuropathic pain associated with CIPN. Additionally, if nicotine appears to have a positive treatment effect, as defined by a ≥ 2.7 point decrease in patient’s total sensory score (baseline compared to treatment and post-treatment scores) of the QLQ-CIPN-20 questionnaire (eg, an improvement in the patients quality of life by one grade), future randomized clinical trials comparing nicotine to other commonly prescribed treatments, such as duloxetine, may be warranted. In addition, further studies of subtype receptor selective agents or of patient population subgroups (based on smoking history, gender, chemotherapeutic agents, or receptor expression level) can be designed.

1.4 Potential Risks and Benefits of the Investigational Treatment

1.4.1 Potential Benefits

The analgesic properties of nicotine and nicotinic agonists have been established in many animal and human studies. Acute nicotine transdermal patch administration could improve patient’s CIPN-associated pain, and thus their quality of life. Further, successful management of patients’ CIPN could circumvent chemotherapy dose reduction and early treatment discontinuation. The use of an FDA-approved, over-the-counter drug with a relatively safe short-term use profile would greatly accelerate the clinical development of this as a pain management strategy. Finally, if successful, this study would stimulate the development of targeted agents that interact with subtypes of nAChRs, which might act with fewer side effects.

1.4.2 Potential Risks

One of the challenges with the use of nicotine as a therapeutic agent relates to the potential side effects of nicotine on nicotine-naïve patients (ie, patients with no nicotine use history). Related symptoms experienced by non-smokers being treated with a nicotine transdermal system include nausea, dizziness, vomiting, minor skin irritations, and palpitations (23). There is also a risk for the development of nicotine dependence for current non-smokers and a recurrence of nicotine dependence for previous smokers. Overall, the published side effects for a 15mg or less nicotine transdermal patch were reported as mild and tolerable (24-27). Nonetheless, we will evaluate the safety and toxicity of nicotine transdermal patch administration in a population of non-smokers experiencing CIPN as described in our secondary outcome measures.

2 OBJECTIVES

[figure not shown]
2.1 Primary Objective

Assess the efficacy of short-term nicotine transdermal patch administration for the treatment of CIPN in cancer stable patients or patients in remission.

2.2 Secondary Objectives

Secondary objectives include:

- 2.2.1 Assess pain-related functional interference associated with nicotine transdermal patch administration for the treatment of CIPN in patients whose cancer is stable or in remission.
- 2.2.2 Assess the AEs profile of nicotine transdermal patch administration for the treatment of CIPN in patients whose cancer is stable or in remission.

3 STUDY DESIGN

3.1 General Description

This phase 2 study will test the efficacy of short-term transdermal nicotine transdermal patch administration in patients who have been diagnosed with CIPN. The study will follow an open-label, crossover within-subjects clinical trial design with nicotine transdermal patch concentrations of 7 mg and 14 mg.

[figure not shown]
3.2 Primary Endpoint

Efficacy of short-term nicotine transdermal patch administration in the treatment of CIPN in patients whose cancer is stable or in remission as defined by a ≥ 2.7 point decrease in the total sensory score of the EORTC QLQ-CIPN-20 (eg, an improvement in the patients quality of life by one grade).

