4.1.2 CIPN characteristics

4.1.2.1 Clinically diagnosed peripheral sensory neuropathy defined as:

4.1.2.1.1 Greater than Grade 1 peripheral sensory neuropathy using the CTCAE v5.0 grading scale

- **Grade 1** Asymptomatic
- **Grade 2** Moderate symptoms; limiting instrumental activities of daily living (ADL)
- **Grade 3** Severe symptoms; limiting self-care ADL
- **Grade 4** Life-threatening consequences; urgent intervention indicated

AND

4.1.2.2 Have a baseline CIPN PRO total sensory score ≥ 24.3 on a 19 to 76 scale using the EORTC QLQ-CIPN-20 questionnaire

AND

4.1.2.3 Have a CIPN-related neuropathic pain score ≥ 4 on a 0 to 10 scale using the Brief Pain Inventory-Short Form (BPI-SF) item 5

Note: Patients currently being treated for CIPN will not be excluded and are allowed to continue their treatment and current treatment dose while on study.

4.1.3 Will not have used any nicotine or tobacco products (eg, cigarettes, electronic cigarettes, smokeless tobacco, or other nicotine replacement therapies) within 14 days prior to study treatment start date

4.1.4 Eastern Cooperative Oncology Group (ECOG) performance status of 0, 1, or 2 (see [Appendix 1](#))

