10 MEASUREMENT OF EFFECT

10.1 Evaluation of Transdermal Nicotine Patch Efficacy

CIPN PROs will be measured using the EORTC QLQ-CIPN20 sensory subscale score. The QLQ-CIPN20 numerical score has a range of 19-76, in which lower scores indicate less symptoms and a better quality of life. The scores can also be converted to a scale of 0 to 100, in which higher scores indicate less symptoms and better quality of life. A recently published study provides validity and guidance as to how to interpret QLQ-CIPN20 scores (18). Utilizing this study's reported numerical relationship between QLQ-CIPN20 scores and peripheral sensory neuropathy CTCAE grades (initially reported using CTCAE grade v4.0) as a hypothetical guide (See [Table 2](#)), we can estimate how many QLQ-CIPN20 score points are needed to decrease the CTCAE score by 1 grade. Using the 19-76 numerical scale for QLQ-CIPN20, a minimum decrease of 2.7 points (range of 2.7-5.6 points) would be required to improve a patient's quality of life by one grade (grade 2 to grade 1).

Table 2. Reported/Suggested Numerical Relationship Between CTCAE v4.0/v5.0 and EORTC QLQ-CIPN-20 Scores.

Peripheral Sensory Neuropathy CTCAE v5.0	EORTC QLQ-CIPN20 (Scale 19-76)
Grade 0	21.6
Grade 1	24.3
Grade 2	29.9
Grade 3	33.6

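### The 2.7-point success threshold is a gap between grade-level scores that the plan's own table places at a different grade step, and the PGIC taken at the same visits is not used to check it

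*Combined protocol and SAP*

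**What the plan says.** Section 3.2 sets the primary endpoint as at least a "2.7 point decrease in the total sensory score of the EORTC QLQ-CIPN-20 (eg, an improvement in the patients quality of life by one grade"). Section 1.3 applies the same figure to each patient's own course, as a 2.7 "point decrease in patient’s total sensory score (baseline compared to treatment and post-treatment scores"), and says that a positive result may justify randomised trials.

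The figure comes from Section 10.1. Using a published relationship between score and grade, the plan says "we can estimate how many QLQ-CIPN20 score points are needed to decrease the CTCAE score by 1 grade". Table 2, titled "Reported/Suggested Numerical Relationship Between CTCAE v4.0/v5.0 and EORTC QLQ-CIPN-20 Scores", gives 21.6, 24.3, 29.9 and 33.6 for Grades 0 to 3. The text then says that a minimum decrease of 2.7 points (range 2.7 to 5.6) "would be required to improve a patient's quality of life by one grade (grade 2 to grade 1"). Section 13.1 (Sample Size and Accrual) repeats this. Section 10.1 describes the relationship as hypothetical. Section 1.3 describes the underlying evidence as an association, "whereby patients with higher CTCAE grade had worse QLQ-CIPN20 scores".

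Section 4.1.2 admits patients with "Greater than Grade 1 peripheral sensory neuropathy using the CTCAE v5.0 grading scale" and a baseline score of at least 24.3.

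On the PGIC, Section 1.3 says: "This study will use a version of the PGIC adapted to patients with CIPN". It rates upper and lower extremities separately and is an exploratory outcome. Tables 3 and 4 schedule it at Cycle 1 Day 8, Cycle 2 Day 1, Cycle 2 Day 8 and follow-up Day 8 to 15. Section 13 mentions it only in the evaluability rule (13.4.2).

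**The concern.** A table of typical scores by grade shows how far apart the grades lie. It does not show how far one patient's score must fall before that patient is better. Sections 3.2 and 1.3 nevertheless use a gap from such a table as improvement within a patient, and the caution expressed in Section 10.1 does not carry over to the endpoint definition.

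The grade label is a separate problem: the step named in the text is not the step that yields 2.7 in the table.

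At stake is interpretation. If the plan is followed as written, a mean fall of about 2.7 points could be reported as a one-grade improvement and used to argue for a randomised trial, although nothing in the plan supports that equivalence. The trial collects patients' own ratings of change at the same visits, which could show whether a fall of this size goes with perceived improvement, but no analysis links the two.

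**Working it through.** **1. Where 2.7 comes from.** Differences between adjacent rows of Table 2 (Section 10.1):

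| Step | Arithmetic | Gap |
|---|---|---|
| Grade 1 to 0 | 24.3 - 21.6 | 2.7 |
| Grade 2 to 1 | 29.9 - 24.3 | 5.6 |
| Grade 3 to 2 | 33.6 - 29.9 | 3.7 |

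Only the Grade 1 to 0 step gives 2.7. The step named in Sections 10.1 and 13.1 gives 5.6. Patients eligible under 4.1.2 start above Grade 1, where the listed gaps are 5.6 and 3.7.

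**2. What kind of numbers these are.** If the score is a sum of whole-number item ratings (an assumption), one patient cannot score 21.6 or 24.3, so the table values are group summaries. Together with the wording in Section 1.3, this points to a comparison across patients. The documents do not say so outright.

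**3. The plan's own sample size.** Inputs from Section 13.1: effect size 0.54, 5% level, power at least 95%, n = 47. Exact paired-t power (noncentral t, 46 df, noncentrality 0.54 x sqrt(47)) is 95.2% two-sided, and 47 is the smallest n that reaches 95%. One-sided, as in Section 13.2.1, power is 97.7%. The figure reproduces. The implied SD of change is 2.7 / 0.54 = 5.0; the plan does not state an SD.

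**4. Does the planned test check the threshold?** Section 13.2.1 gives a one-sided paired t-test and no 2.7-point null. Taking the null as zero, the smallest significant mean decrease is t(0.95, 46) x SD / sqrt(47) = 1.679 x 5.0 / 6.856 = 1.2 points (0.7 at SD 3, 2.4 at SD 10). A significant result therefore does not by itself show a fall of 2.7.

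**5. How precise a PGIC comparison would be.** The 95% half-width of mean change in a category of k patients is t(0.975, k-1) x SD / sqrt(k). With SD 5.0:

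- k = 15: 2.145 x 5.0 / 3.873 = 2.8
- k = 20: 2.093 x 5.0 / 4.472 = 2.3
- k = 30: 2.045 x 5.0 / 5.477 = 1.9

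The widths scale with the SD: for k = 15 to 30 they are 1.7 to 1.1 at SD 3 and 5.5 to 3.7 at SD 10. A PGIC-anchored threshold cannot be calculated now, because the documents give no data on within-patient change and no correlation with PGIC.

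**The case against.** The plan is already cautious. Section 10.1 calls the relationship hypothetical, Section 1.2 calls the trial proof-of-principle, and Section 1.3 says only that further trials may be warranted. This stands in part, but Section 3.2 carries no such caveat.

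The quoted range of 2.7 to 5.6 could be read as the smallest and largest gaps in the table, with 2.7 as the least demanding. The entry score of 24.3 is also the table's Grade 1 value, so a patient near that floor who fell by 2.7 would reach the Grade 0 value. Neither point rescues the label: the text names Grade 2 to Grade 1, and the CTCAE criterion excludes Grade 1 patients.

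Section 13.2 covers primary and secondary endpoints only, so the PGIC is treated like the other exploratory items. PGIC is also an imperfect anchor: two extremity ratings, no stated reference period, the same open-label expectation, and too few patients per category to re-estimate a threshold. All of this stands. It limits the remedy to a descriptive check.

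A reader might infer that about 29% of patients would meet the threshold by chance, since Phi(-2.7 / 5.0) = 0.29 (18% to 39% for SD 3 to 10). This illustrates a per-patient reading with zero mean change and normal differences. It is not an error rate of the planned test, which concerns the mean. With zero true change, n = 47 and SD 5.0, a mean fall of 2.7 lies at z = 2.7 / (5.0 / sqrt(47)) = 3.70, a probability of about 0.0001. Nor is it the rate among patients who report no change, since the SD mixes noise with real differences between patients.

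**Conclusion.** The point holds in limited form. The 2.7-point threshold has no within-patient support in the documents, its stated grade step disagrees with Table 2 (2.7 against 5.6), and the PGIC data that could qualify it have no planned use.

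Two stronger readings are not supported. It is not established that Table 2 compares means of different patients: the documents do not say whether one patient contributed at several grades, so this remains an inference from the non-integer values and the wording of Section 1.3. Nor is the trial mis-sized: n = 47 reproduces, and at the implied SD of 5.0 the larger gaps of 3.7 and 5.6 would be easier to detect than 2.7.

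The grade mismatch follows from the table alone. The precision figures rest on the implied SD. The consequence is for interpretation, and the priority is low to optional.

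**What to change.** 1. In Sections 1.3, 3.2, 10.1 and 13.1, describe 2.7 as a provisional threshold. Correct or remove the one-grade, Grade 2 to Grade 1 equivalence so that the text agrees with Table 2.

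2. Add to Section 13.2 a supportive descriptive analysis at Cycle 1 Day 8 and Cycle 2 Day 8. Report the correlation of QLQ-CIPN20 change with PGIC and, with PGIC collapsed to better / no change / worse, the mean change with 95% CI and the proportion falling by at least 2.7. State in advance how the upper- and lower-extremity ratings are used, and which QLQ-CIPN20 baseline matches the PGIC reference period. At Cycle 2 Day 8 that could be screening or Cycle 2 Day 1.

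3. Use the result to qualify the reading of the primary mean change, not as a replacement threshold.

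The cost is some rewording and one extra table from data already scheduled, with no new visits and no change to the primary test or sample size. The downside is imprecision (about +/-1.9 to 2.8 points for 30 to 15 patients per category at SD 5.0), and the PGIC shares the open-label expectation effect.
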